### 3.0 Study objectives and endpoints

#### 3.1 Study hypothesis

It is hypothesised that increasing the pulsative frequency (0-100 Hz) produced by the NMN device will improve deposition within the sinuses.

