#### 3.2 Primary objective and endpoint

The main objective of the study is to determine the optimal frequency for the NMN that will provide the basis for future *in vivo* sinus targeting of drug delivery systems. The primary endpoint of this study is the total area of distribution (mm^2) of radiolabelled saline immediately after administration by the NMN (T0) in the different regions of the sinus cavity.

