#### 3.3 Secondary objectives and endpoints

The secondary objectives are:

1) To generate an anatomically correct model of the upper respiratory tract that includes the sinus cavities (maxillary, frontal, ethmoidal, sphenoidal) and that could be used for *in vitro* optimisation study of sinus delivery formulation in the future.

It is expected to obtain from all participants a high-resolution CT scan of their head at the first initial visit that includes sinus structure allowing for realistic *in vitro* simulation and optimization for sinus delivery in the future.

2) To assess the clearance of the radio-labelled saline over 1 hour (at 0, 20 and 60 minutes post-administration) after its administration with the NMN prototype at four different pulse frequencies.

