#### Interpretation and assumption of quantitative data

The quantitative assessment of nasal deposition, retention and clearance will be determined as a percentage of total nasal deposition (quantified using the first planar image immediately after inhalation of the radioaerosol) as a function of intensity within defined areas of the nasal cavity, left and right of the maxillary, frontal, ethmoidal and sphenoidal sinuses using standard protocol as briefly described below. Count rates in the selected region of interests will be analysed using the MATLAB Software or ImageJ Software packages (<http://rsb.info.nih.gov/ij/>). Count rates will be corrected for background activity and radioactive decay.

For analysis of the distribution of the radiolabelled saline into the different compartments, all serial images will be superimposed with regions of interest (ROI) of the nasal airways and sinuses defined as shown in Figures 6 and 7. The activity is obtained in these ROIs.

[figure not shown]

Figure 6. Regions of interest of the nasal cavity of the right and left maxillary and frontal sinuses (MR, FR, FL and ML). Image was taken from [9].

The primary endpoint of this study is the total area of distribution ( $\text{mm}^2$ ) of radiolabelled saline immediately after administration by the NMM ( $T_0$ ). This will be evaluated for each of subsites (surgically expanded ostia of the paranasal sinuses and oropharynx) and compared between treatments (A-D) which correspond to the different pulse frequencies tested. Between-treatment differences in total area of deposition of radiolabelled saline at each subsite will be compared by means of one-way analysis of variance (ANOVA) with application method as a factor.

Pairwise comparisons will be performed between each of the pulsed application methods and the continuous application (no pulse). Pairwise comparisons will be tested using a two-tailed p-value of  $<0.05$ .

Clearance will be calculated by the decrement in total radiolabelled saline between  $T_0$ ,  $T_{20}$  and  $T_{60}$ . Clearance will be evaluated for each subsite and compared between treatments (A-D). As with the primary efficacy endpoint, between-treatment differences in radiolabelled clearance will be tested by means of one-way analysis of variance (ANOVA) with application method as a factor. Pair-wise comparisons will be made between each of the pulsed application methods and the continuous application (no pulse).

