The retention of radiolabelled saline will be evaluated as the Area Under the Curve between  $T_0$  and  $T_{60}$  ( $\text{AUC}_{0-60}$ ) of the following assessments:

- the total area of deposition of radiolabelled saline
- the intensity of radiolabelled saline

The AUCs will be evaluated for each subsite and compared between treatments (A-D). Between-treatment differences in AUCs will be tested by means of one-way analysis of covariance (ANCOVA) with application method as a factor and the value at  $T_0$  as

covariate. Pair-wise comparisons will be made between each of the pulsed application methods and the continuous application (no pulse).

[figure not shown]

Figure 7. Example of superposition of anterior gamma camera images of radiolabelled aerosol after nasal delivery [9]. After deletion of the activity in the central nasal cavity, the aerosol penetration into the sinuses will be highlighted in B and D.

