## 4.0 Study design

### 4.1 Type of study

This is a single centre, randomised, controlled, cross-over clinical study investigating the deposition of aerosols generated by the NMN prototype into the nasal cavity using different pulse frequencies.

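### The AUC0-60 retention analysis adjusts for the post-dose T0 value, so it removes most of any exposure difference that arises through deposition and can produce false retention differences

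*Protocol*

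**What the plan says.** Protocol section 3.4 (Interpretation and assumption of quantitative data) states: "The retention of radiolabelled saline will be evaluated as the Area Under the Curve between" T0 and T60, for both area and intensity, at each subsite. Differences between settings are tested by "one-way analysis of covariance (ANCOVA) with application method as a factor and the value at" T0 as covariate, followed by a comparison of each pulsed setting with continuous delivery. For the primary endpoint the same section says: "Pairwise comparisons will be tested using a two-tailed p-value of" less than 0.05; I apply that level here.

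Four other places bear on the covariate:

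- Section 3.2: "The primary endpoint of this study is the total area of distribution", taken as the area of "radiolabelled saline immediately after administration by the NMN". T0 is therefore post-dose, and its area version is the primary endpoint.
- Section 3.1 hypothesises that "increasing the pulsative frequency (0-100 Hz) produced by the NMN device will improve deposition within the sinuses".
- Section 3.3 sets the imaging times "at 0, 20 and 60 minutes post-administration", so T0 is the first ordinate of the AUC.
- Section 4.1 describes a "randomised, controlled, cross-over clinical study". Section 4.3 asks for 11 completers.

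The protocol does not say whether the target is total exposure over the hour or retention given the initial deposit.

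**The concern.** Covariate adjustment is safe when the covariate cannot be affected by the randomised condition. Here the covariate is a result of the pulse setting. Adjusting for it removes the part of the AUC difference that comes through deposition, so the contrast does not measure exposure. It measures relative retention only if a common straight line on T0 recovers proportionality between AUC and T0. Error in T0 flattens that line. A participant-level link between deposition and clearance tilts it. In either case a setting that changes T0 can appear to change retention when the tracer leaves at the same rate at every setting.

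At stake is the reading of the retention results when settings are compared for later sinus delivery.

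**Working it through.** The protocol states no figure to reproduce. Everything below the first step rests on assumed inputs.

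**1. Share of T0 in the AUC.** With images at 0, 20 and 60 minutes the trapezoid weights are 10, 30 and 20. For exponential clearance at rate k, AUC/T0 = c = 10 + 30e^(-20k) + 20e^(-60k). Section 6.3.1 gives a half-life of about 70 minutes, but for lung, so I take it only as an assumption:

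- 70 min: c = 10 + 24.6 + 11.0 = 45.7; share of T0 = 10/45.7 = 22%
- 20 min: c = 10 + 15 + 2.5 = 27.5; share 36%
- 140 min: c = 10 + 27.2 + 14.9 = 52.0; share 19%

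**2. Why the slope falls short.** Let v be the variance of true T0 among participants within a setting and e the reading-error variance (log scale, errors independent over time). The fitted slope is about b = (c·v + 10·e)/(v + e). With equal fractional clearance the true AUC difference is c·ΔT0. The adjusted contrast is then (c − b)·ΔT0, which as a share of the true difference is

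[e/(v + e)] × (1 − 10/c).

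Assume k = 0.02/min, so c = 10 + 20.1 + 6.0 = 36.1. Assume between-participant SD 0.4 and visit SD 0.2, so v = 0.16 + 0.04 = 0.20, and CV 20%, so e = 0.04. The share is (0.04/0.24) × 0.723 = 12%. Simulation with T0 doubled gives an exposure difference of +100% and an adjusted difference of about +14%, where the true retention difference is 0.

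**3. False retention differences, ANCOVA as written.** Same inputs: 11 participants, four settings, participant SD of clearance 20%, no deposition-clearance link, nominal 5%.

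| T0 ratio | Reading CV | Error over time | ANCOVA as written |
|---|---|---|---|
| 1.0 | 20% | independent | 3% |
| 1.25 | 20% | independent | 5% |
| 1.5 | 20% | independent | 10% |
| 2.0 | 10% | independent | 11% |
| 2.0 | 20% | independent | 21% |
| 2.0 | 30% | independent | 30% |
| 2.0 | 20% | 50% of variance shared | 12% |
| 2.0 | 20% | 80% of variance shared | 8% |

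Log(AUC/T0) with participant and setting terms stays at about 5% under independent error. The rejection rates mix bias with unequal residual spread, since AUC scatter grows with the deposit; the +14% in step 2 is the bias itself.

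**4. A second set of inputs.** Between-participant SD 0.20, visit SD 0.15, SD of log clearance rate 0.10, half-life 70 min, T0 ratio 1.5, proportional error, no link:

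| T0 error | Unadjusted AUC contrast | ANCOVA contrast | Removed | False positives | Log ratio |
|---|---|---|---|---|---|
| 0 | 2,353 | 2 | >99% | 4% | 5% |
| 5% | 2,358 | 76 | 97% | 8% | 5% |
| 10% | 2,357 | 269 | 89% | 15% | 5% |
| 20% | 2,406 | 769 | 68% | 33% | 5% |

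A smaller spread of true T0 makes the same error matter more: 33% here, against 10% in step 3 at the same ratio and CV.

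**5. Link between deposition and clearance.** Suppose participants who deposit more also clear faster (+0.3 on the log rate). With error-free T0 the ANCOVA contrast is +568 and the false-positive rate 93%. If they clear more slowly (−0.3), the contrast is −526 and the rate 94%. The sign follows the link. Measurement error then adds or offsets: at −0.3 with 20% error the contrast is +447 and the rate 11%.

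**The case against.** Several objections have force.

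- **The false differences are conditional.** A reader might infer that the ANCOVA creates them as a matter of course. It does not: they need a setting effect on T0 together with error in T0 or a link to clearance. The first condition is the study's own hypothesis, but no document gives its size or the imaging error, so only *can* is supportable.
- **The direction is not fixed.** A reader might infer that the higher-depositing setting is always favoured. That holds under measurement error alone, but a deposition-clearance link can reverse it.
- **Errors may be shared.** Section 3.4 lays the same regions of interest over all serial images, so placement error is plausibly common to the three times. Shared error does not flatten the slope, and the rates fall accordingly.
- **Allowing for the initial deposit is a fair aim.** The protocol calls the AUC retention, not exposure. Dropping T0 and doing nothing else would turn the retention test into a second deposition test.
- **The deposition difference is not hidden altogether.** T0 area is tested unadjusted as the primary endpoint, and the decrement over time is tested unadjusted as clearance. Only an unadjusted AUC contrast is missing.
- **Intensity is already scaled** to the total nasal deposit on the first planar image. Over the whole nasal cavity a further division by T0 largely repeats this. At a sinus subsite the scaled T0 value can still differ by setting, and area is not covered by that scaling.
- **The stakes are limited.** The study is exploratory, and retention AUC is not among the endpoints in sections 3.2 and 3.3.

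These points narrow the claim. They do not make T0 a baseline, and they do not give the adjusted contrast a clear meaning for area or for the sinus subsites. A statistical analysis plan may exist, but the protocol itself fixes this model.

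**Conclusion.** The point holds in conditional form. That T0 is post-dose, expected to vary by setting, the primary endpoint for area and part of the AUC follows from the protocol without any assumption. In every as-written case in steps 2, 4 and 5 where the setting raised T0, the adjustment removed more than half of the exposure difference; without a link it removed 64% to over 99% (the lower end with 30% additive error in T0).

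The false-positive rate is a range. Under the step 3 inputs it is about 3-5% with no or a small T0 effect, 10% at a ratio of 1.5 with CV 20%, and 11-30% at a ratio of 2 with CV 10-30%. It is 8-12% at CV 20% if most or half of the error variance is shared. It is higher with less spread in T0 or with a deposition-clearance link.

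One warning concerns a partial repair. Adding a participant term while keeping the covariate leaves only the noisier within-participant slope and can make matters worse: from 21% to about 54% at ratio 2 and CV 20%. That figure does not describe the planned analysis, which has no such term.

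**What to change.** In section 3.4, remove T0 as a covariate and name two quantities, each compared between settings within participant:

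1. Exposure: AUC0-60 without T0 adjustment, at each subsite.
2. Relative retention: log(AUC0-60/(60 × T0)), for the pooled sinus region and for other regions with adequate T0 activity.

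This takes two sentences and no new data. There are three costs:

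- Relative retention cannot be estimated at subsites with almost no activity at T0, where only the first quantity is reported.
- Some power is lost when settings do not differ at T0. With clearance slowed to 0.7 times, the ratio detected it in 32% of runs against 37% for the ANCOVA at 10% error, and in 10% against 14% at 20% error.
- With additive rather than proportional error, the unlogged ratio's false-positive rate was 4.3-8.2%, so it is not exact in every case.

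For area, nothing in the protocol says that mm² falls in proportion to its T0 value, so there the ratio should be read as descriptive.

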### 3.5 Safety Assessment

Adverse events (AEs) will be collected for all randomized participants and will be listed with type of AE, severity and relationship for each treatment group, using the safety population. Adverse events data will be summarized for each treatment groups using frequencies and percentages (% of participants with each specific AE)

## 4.0 Study design

### 4.1 Type of study

This is a single centre, randomised, controlled, cross-over clinical study investigating the deposition of aerosols generated by the NMN prototype into the nasal cavity using different pulse frequencies.

### 4.2 Study design

This study will be performed in healthy Caucasian male participants with no history of sinusitis or chronic respiratory diseases.

Informed consent will be obtained for participants prior to the initiation of any study-specific procedures including screening. All participants will receive a head CT scan on their first visit.

The treatment sequence for the study participants will then be randomly applied with at least a 72-hours washout period between treatments (Table 1). The potential carry-over effect of the applied radiolabel is considered negligible since Technetium has a half-life of 6 hours, consequently a 'rest' minimum period of 72 hours is considered sufficient between imaging study days.

*Table 1. Treatment types to applied in the proposed study*

Treatment	Device	Application method
A	NMN	No pulsing (continuous mode)
B	NMN	10 Hz pulse
C	NMN	50 Hz pulse
D	NMN	100 Hz pulse

Each participant will receive a radio-labelled saline dose of 2.0 mL per visit by one of the application methods (Table 1), the order of which will have been randomly selected.

Nasal deposition, retention and clearance of radiolabelled saline solution will be measured using serial imaging of SPECT/PET and gamma scintigraphy. The study does not involve the use of novel treatments and is restricted to investigating the ability of the NMN device to target the paranasal sinuses.

#### **4.3 Number of participants**

Employing a cross-over design enables each participant to act as its own control, and reduces the overall number of patients needed to assess aerosol deposition.

For this investigational study, participants who meet all the eligibility criteria will be enrolled and randomised into the study until 11 participants who complete the study are met.

#### **4.4 Number of centres**

All testing and recruitment will be performed at RNSH.

#### **4.5 Expected duration of the study**

Participant recruitment is expected to be completed within 6 months of approval from the relevant HRECs. The testing phase will begin right after the participant-screening visit, and all testing will be completed within 60 days of commencement. In all, the anticipated finish date will be December 2017- No ongoing follow-up will be conducted.

## **5.0 Study population**

## 5.1 Sample size calculation

A previous study that investigated the temporo-spatial deposition of saline delivered by a squeeze bottle, nasal saline spray and nasal gel enrolled 5 healthy subjects (**Bleier et al. 2011**). Similarly, a PARI VibrENT nebulizer system that evaluated the pulsating aerosol (fixed frequency of 25 Hz) to the sinuses was conducted with five healthy volunteers (**Moller et al 2010**). Taking into account that four different pulse frequencies are evaluated a sample size of minimum 10 subjects will be sufficient for this pilot study.

## 5.2 Recruitment and screening

Potential participants will be identified from the RNSH database of trial participants. Each of these volunteers has previously consented to be included in the database, and to be contacted for future studies.

The study will also be advertised through the WIMR website and social media pages where brief description of the study will be posted. No other media advertising is planned. The WIMR media officer will coordinate advertisement of the trial. However, recruitment will still be performed at the RNSH.

Initial pre-screening will be made via telephone, where the volunteer will be provided with verbal information about the study and the inclusion/exclusion criteria. If the volunteer is willing to participate in the study, they will be invited to attend an enrolment visit at RNSH.

## 5.3 Eligibility criteria

### 5.3.1 Inclusion criteria

Signed informed consent will be obtained before any study procedure. Patients must be able to understand and be willing to sign a written informed consent.

Inclusion criteria, which must be met at the time of study screening, are:

- Healthy Caucasian male
- Aged >20 years
- No history of smoking
- No history of chronic lung diseases including asthma, cystic fibrosis, tuberculosis, chronic obstructive lung disease
- Normal lung function with stable and reproducible baseline FEV1 of > 80% of predicted value following adjustment for height, age and gender according to the Global Lung Initiative equation [18].
- No history of chronic sinusitis or rhinitis
- Agree that CT scan data can be used post-study to generate an anatomically correct model of the upper respiratory tract

### 5.3.2 Exclusion criteria

Exclusion criteria are:

- Significant upper and lower respiratory infection within the previous 4 weeks
- History of chronic sinusitis or rhinitis
- History of recurrent lung infections.
- History of chronic lung diseases
- History of severe or multiple allergies, including hay-fever and perennial rhinitis
- History of nasal fracture, nasal deformities or nasal polyps
- History of disease, surgery, or abnormality of the upper respiratory tract, especially the nasal cavity.
- History of significant nose bleeds
- Participants using topical nasal medication e.g. decongestant, within the last 14 days of the first study day
- Participants unable to perform pulmonary function test according to ATS/ERS criteria
- Participants with documented or suspected, clinically significant alcohol or drug abuse
- Current malignant or cardiovascular disease
- Any serious or active medical or psychiatric illness
- Current smokers, i.e. those who had smoked within the last 12 months and 6 hours prior to the scan. A negative Cotinine test must be demonstrated at each visit.
- Participants who have any non-removable metal objects such as pacemakers, insulin/infusion pumps, cochlear and ear implant, metal plates, screws etc. in their head, neck, chest or abdominal area that may interfere with the /PET/SPECT/CT.
- Nasal jewellery or nasal piercing
- Participants with tattoos or permanent makeup above shoulder
- Participants for whom participation in this study will exceed the limit of total radiation exposure allowed in any 12 months period (5 mSv), or will exceed 10 mSv over the last five-year period [19].

### 5.4 Informed consent process

Participants will be presented with written information on the study process, the study device and assessments, and potential side-effects. If the study investigator judges them capable of providing informed consent, the participant will be asked to provide written consent. The ability to understand written and verbal English is included in this assessment.

## 5.5 Enrolment

If written informed consent is provided, the participant will be allocated a unique participant identification number, which will be recorded in the WIMR Respiratory Technology, Airways Physiology and Imaging Group list of trial participants. This number will appear on all study documents and computer files, and will be used as the identifier during data analysis until the study is completed.

## 5.6 Randomisation

Randomisation will occur once participant eligibility is confirmed.

Participants will be randomly assigned to one of the four possible study treatment frequencies in a fashion that ensures: that each individual receives each treatment.

The randomisation sequence will be generated by computer, prior to the study, by an independent statistician. The statistician will maintain a schedule of participant numbers and drug sequence allocation.

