## 6.0 Trial procedure

### 6.1 Research plan

The study will have a cross-over design with each participant completing 4 different device settings over a period of 4 visits with at least a 72 hour wash-out period in between visits.

[figure not shown]
In the first visit, participants will sign a written informed consent, undergo lung function, urinary cotinine and skin prick tests, as well as completing 2 standard and validated clinical questionnaires: Woolcock's Clinical questionnaire and SinoNasal Outcome Test (SNOT) 22 [20] on medication use, medical history and smoking history. Participants will then undergo a full head high-resolution CT scan of the upper respiratory tract before being subjected to 1 of 4 randomised treatments of radio-labelled saline by using the NMN: A) no pulse frequency (continuous delivery mode), B) 10 Hz pulse frequency, C) at 50 Hz pulse frequency, or D) at 100 Hz pulse frequency. Immediately following administration of the radio-labelled aerosol, deposition of aerosols will be measured via gamma camera and dynamic SPECT/PET images for the first 20 minutes and finally at 1 hour to assess deposition, retention and clearance.

[figure not shown]
In subsequent visits (2-4), participants undergo a brief medical interview as well as repeating the urinary cotinine tests to confirm non-smoking status before further administration of radio-labelled aerosol via one of the four treatment processes as defined by the randomisation sequence.

Prior to the initiation of the screening assessments, potential participants will be given a complete explanation of the study.

Once an individual has agreed to participate and signed a copy of the Informed Consent documents, information will be obtained from the participant to determine their eligibility for enrolment in the study

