## 6.2 Study flow chart

### 6.3 Schedule of study assessments

Table 2. Schedule of assessments

Assessment	Screening+ Visit 1*	Visit 2	Visit 3	Visit 4
Informed consent	x			
Inclusion/exclusion criteria	x			
Medical history	x			
Brief medical Interview		x	x	x
Concomitant medications	x	x	x	x
Weight and height	x			
Skin prick test	x			
Urinary cotinine	x	x	x	x
Spirometry	x			
Treatment randomisation*	x			
Head CT Scan	x			
Intervention (A-D)	A or B or C or D	A or B or C or D	A or B or C or D	A or B or C or D
Radiation Dose (mSv)	1.9 + 0.24	0.24	0.24	0.24
Deposition and clearance study (SPECT or PET and gamma scintigraphy)	x	x	x	x
Adverse event assessments & monitoring	x	x	x	x

\* Screening and first treatment performed on same day

\*\* Randomisation of treatment to define order of administration

Nasal Deposition by NMM

Clinical trial  
HREC number: HREC/16/HAWKE/256

Trial protocol Version: 2.0  
Number: RT16-NMN-V01 /  
AFT-MD-01

Version 2

Date: 23 September 2016

Page: 23 of 31

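### Section 5.6 does not require frequencies to be balanced over visits, and the stated one-way ANOVA has no participant or visit term to correct an imbalance

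*Protocol*

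**What the plan says.** The trial is a four-period crossover, with "each participant completing 4 different device settings over a period of 4 visits" (section 6.1), run "until 11 participants who complete the study are met" (section 4.3).

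On allocation, section 5.6 says "Participants will be randomly assigned to one of the four possible study treatment frequencies" and adds that this is done "in a fashion that ensures: that each individual receives each treatment". It also says "The randomisation sequence will be generated by computer, prior to the study, by an independent statistician". Section 4.2 says of the application methods only that each participant has one per visit, "the order of which will have been randomly selected". The protocol names no sequence set, Latin or Williams square, blocking scheme or balance over visits. Section 5.9 replaces participants who withdraw between the first and last treatment, but does not say which sequence the replacement receives.

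On analysis, section 3.4 (Interpretation and assumption of quantitative data) compares frequencies by "one-way analysis of variance (ANOVA) with application method as a factor", followed by pairwise comparisons of each pulsed mode with continuous mode. Application method is the only factor named.

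On visits, the footnote to Table 2 reads "Screening and first treatment performed on same day". Spirometry, the skin prick test and the head CT are scheduled at visit 1 only.

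**The concern.** In a crossover with one treatment per visit, balance of treatment over visits is what keeps a visit effect out of the treatment comparisons. Here the allocation rule works only within the participant, and the stated model cannot adjust for visit. If results at one visit differ systematically from the others, part of that difference passes into the frequency comparisons, in proportion to the imbalance.

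A visit effect is plausible but not documented. Visit 1 carries the screening procedures and is the first use of a device triggered by the participant's own exhalation (section 6.3, Treatment processes and Imaging), so practice could matter. The washout argument in section 4.2 covers residual radioactivity only: 72 h is 12 half-lives of 6 h.

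At stake are the three comparisons with continuous mode that inform the main objective in section 3.2, the choice of an optimal frequency.

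**Working it through.** **Inputs.** Four frequencies and four visits (section 6.1); 11 completers (section 4.3); three contrasts with continuous mode and a one-way model (section 3.4). The protocol gives no SD, effect size or visit effect, so there is no stated figure to reproduce.

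**Assumption.** Each participant independently receives one of the 4! = 24 orders with equal probability. This is a plain reading of the one stated constraint, but not the only list that would comply.

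**1. Counts per frequency and visit.** The ideal count is 11/4 = 2.75 in each of 16 cells.
- One given frequency is never given at visit 1 with probability 0.75^11 = 4.2% (exact).
- Some frequency is never given at some visit, over all 16 cells: about 50% of simulated draws (49% to 50% across runs of 20,000 to 100,000). With 10 participants this is 60%, with 12 it is 40%.
- Some frequency is given to 6 or more of the 11 at one visit: 42%.

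**2. Share of a visit-1 effect absorbed by a contrast.** Let visit 1 shift the outcome by δ, and let f be the fraction of participants who receive a frequency at visit 1. Without a visit term,

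bias = δ × (f_pulsed − f_continuous).

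Per participant, the difference of the two visit-1 indicators is +1, −1 or 0 with probabilities 1/4, 1/4 and 1/2. Its mean is 0 and its variance is 1/2. Over 11 participants the SD of the share is √(0.5/11) = 0.213, so the expected bias is zero with an SD of 21% of δ. Simulated absolute shares:

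| Contrast with continuous mode | Median | 90th percentile |
|---|---|---|
| One given contrast | 2/11 = 18% | – |
| Worst of the three | 3/11 = 27% | 5/11 = 45% |

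**3. Participant and visit in the model.** An additive visit effect no longer biases the contrasts. The remaining cost is non-orthogonality. The variance of a contrast relative to a fully balanced layout (2σ²/11) averages 1.12 over 4,000 random layouts, and √1.12 = 1.058, so the standard error is about 5% to 6% larger.

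**4. Williams square.** Cycle the four sequences over 11 completers, giving 3/3/3/2.
- Every frequency occurs 2 or 3 times at every visit.
- The largest visit-1 share difference is 3/11 − 2/11 = 1/11 = 9%.
- The variance ratio is 1.008 for each of the three contrasts.
- Exact balance is impossible because 11 is not a multiple of 4; 12 completers would give 3 per cell.

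**5. Degrees of freedom.** There are 11 × 4 = 44 observations. Error df are 44 − 1 − 3 = 40 in the one-way model, 40 − 10 = 30 with participant added, and 30 − 3 = 27 with visit as well.

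**The case against.** Section 5.6 does not prescribe unrestricted random orders. It gives a minimum condition and leaves the list to an independent statistician, and sequence sets and blocking are often specified in a separate randomisation plan. That stands: a reader might infer that the trial will be unbalanced, and the protocol does not support this. What it shows is that an unbalanced list would comply.

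A reader might also infer that the frequency comparisons are biased by some known amount. They are not: no visit effect is reported, 18% or 27% of an unknown and possibly zero quantity is not a bias estimate, and the expected bias is zero. Participants also actuate the device until the full 2 mL is given, so the nominal volume does not vary with practice, although where it deposits might. The 27% is the worst of three contrasts; 18% is the fair figure for a given one. An empty cell does not by itself bias a contrast or prevent its estimation in an additive model. A standard error 5% to 6% larger is modest in a study that calls itself exploratory and a pilot.

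Most of the harm comes from the missing model terms, and adding participant and visit removes the additive bias whatever the list. That is correct, and it is why the fix has two parts. It does not dispose of the point, because section 3.4 states a specific model and that model has neither term.

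**Conclusion.** The point holds as a weakness in what the protocol requires. The allocation rule does not protect balance over visits, and the stated analysis does not adjust for its absence.

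Under independent, equiprobable orders, the chance of at least one empty frequency-by-visit cell is about one in two. A given contrast would carry a median 18% of whatever visit-1 effect exists. Once participant and visit are fitted, the loss is limited to about 12% in contrast variance on average.

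These figures depend on that assumption about the list, and the bias figures also depend on a visit effect whose size is unknown. Each participant still receives all four settings, so differences between participants are not confounded with frequency. It would also be too strong to say that a period-balanced set abolishes the problem: with 11 completers it reduces the visit-1 share to at most 9% and the inflation to 0.8%. The change is worth making because it is nearly free, not because the results are shown to be distorted.

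**What to change.** In section 5.6, state that participants are randomised in blocks of four to the four sequences of a Williams square, and that each replacement under section 5.9 receives the sequence of the participant replaced. If the list is already built this way, the section need only say so.

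In section 3.4, replace the one-way ANOVA with a model containing participant, visit and frequency, and take the three pairwise comparisons from it.

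The cost is a different computer-generated list, a few sentences of text and some error degrees of freedom: 3 for visit, and 10 for participant, which removes between-participant variation from the error. No additional participants, visits or radiation exposure are needed. Twelve completers would give exact balance, but the fix does not depend on it.
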